
PURPOSE

We propose to conduct the first randomized controlled trial to test whether a cessation intervention in the PED setting can reduce caregiver smoking and decrease children's SHSe.

Primary Aim 1: To evaluate the efficacy of the SBIRT compared to Healthy Habits Control (HHC) condition. Primary outcomes are self-reported prolonged abstinence and point prevalence at 6-weeks and 6-months post-enrollment, validated in all participants via expired carbon monoxide and salivary cotinine. Secondary outcomes include number of cigarettes smoked, quit attempts, readiness to quit, and use of cessation resources.

Hypothesis 1: Caregivers who receive the SBIRT will have higher prolonged abstinence and point prevalence cessation rates compared to caregivers in the HHC condition.

Primary Aim 2: To evaluate the efficacy of the SBIRT on reducing children's SHSe. Outcomes are caregiver reports of total home/car smoking bans and reductions in SHSe (validated using salivary cotinine in children).

Hypothesis 2: Children of SBIRT caregivers will have higher total home/car smoking bans and lower home/car smoking exposure compared to children of HHC caregivers.

Primary Aim 3: To explore mediators and moderators of the SBIRT outcomes.

Hypothesis 3: The SBIRT intervention effect on prolonged abstinence and point prevalence cessation rates will be mediated by the caregiver's perception of the risk of smoking on their child's health and the caregiver's motivation to quit over time. The intervention effect will be moderated and attenuated by factors such as household smokers, financial strain, and low social support to quit.

Secondary Aim 1: To conduct a cost analysis to determine the numbers of SHSe-related PED visits and hospitalizations in children of caregivers in the SBIRT condition compared to children of caregivers in the HHC condition. This will provide a basis for a future, full-scale cost-benefit analysis.

Secondary Aim 2: Using the findings from this project and our prior research, we will develop a manual of operations and a comprehensive package of provider and patient materials that will be disseminated for use in other PEDs and EDs nationwide.

Secondary Aim 3: To quantify the prevalence and identify correlates of Cannabis Smoke Exposure and SHSe among SHS-exposed PED patients.

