7 days via expired carbon monoxide testing and/or salivary cotinine, 2) obtain a follow-up salivary cotinine level on 100% of children to validate total smoking bans, and 3) complete assessment of outcomes. At 6 months, we will assess all caregivers via phone or email. We may contact them via social media or text messaging as well. Participant's privacy will be maintained when contacting them through social media by sending messages that only the participant can see via social media. PHI will not be used on these messages. Should the caregiver report abstinence and smoking bans, a home visit will be conducted to validate self-reported abstinence and total home smoking bans via salivary cotinine on the child and via expired carbon monoxide testing and/or salivary cotinine on the caregivers during home visits. Follow-ups may be conducted at CCHMC hospital if the participant already has a scheduled appointment at the hospital. If study staff is unable to make contact with the family during the course of the study to schedule the follow-ups an unannounced home visit may be conducted in order to complete study procedures.

Randomization. We will stratify by gender of the primary caregiver and stage of readiness to quit smoking where participants will be in stages 1: pre-contemplation, 2: contemplation 1 or 2, or 3: preparation;^{41,42} thus there will be 8 strata for randomization. A random block randomization scheme will be compiled by the study biostatistician prior to the start of the study, and used by the CRC to allocate participants to each condition. The biostatistician has a SAS® program for creating the randomization scheme that has been tested and used for other studies. As it is anticipated that there will be fewer male caregivers, the random blocks used will be smaller than for the females. The randomization scheme will be accessed by the CRC by logging into a dedicated website and entering the gender and readiness to quit stage, the study group assignment and a study identification number will be returned. Backup will be opaque envelopes, kept within the PED with stratification and study identification number marked on the outside.

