3) Intervention Materials: To supplement the baseline intervention, we will provide free caregiver materials used in other healthcare setting (see appendix C). All or some of the materials listed in Appendix C will be provided to the caregiver, as applicable. These materials are downloadable from www.letsgo.org.^{68,91-93} The caregivers will receive email/mail/text messages (caregiver’s preference), for 12 weeks, reminding them of healthy lifestyle behaviors. At 6-weeks we will contact participants via phone calls, emails, text messaging, social media, and home visits to children and caregivers in the SBIRT and HHC condition to: 1) verify abstinence on 100% of caregivers who report that they have not smoked in the past 7 days via expired carbon monoxide testing and salivary cotinine, 2) obtain a follow-up salivary cotinine level on 100% of children to validate total smoking bans, and 3) complete assessment of outcomes. At 6 months, we will contact all caregivers via phone, text messaging, social media or email. Should the caregiver report abstinence and smoking bans, a home visit will be conducted to validate self-reported abstinence and total home smoking bans via salivary cotinine on the child and via expired carbon monoxide testing and/or salivary cotinine on the caregivers during home visits. Follow-ups may be conducted at CCHMC hospital if the participant already has a scheduled appointment at the hospital. If a home visit is not possible, the assessments will be conducted over the phone or via email. An approximately four week window for the follow-up assessments will be used.

At the study’s conclusion, the HHC group will be given brief information regarding resources for quitting smoking over the telephone. A script will be used by the research coordinator to provide this information.

Screening for missed eligible patients

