11. Clinical and cost data. We will be evaluating the clinical characteristics and associated costs/charges of the baseline visit and hospitalization (if the child is hospitalized) and any SHSe-related or other visits or hospitalizations for the period up to 12 months prior and/or 12 months after the baseline visit. We will extract clinical data and costs from the charts that may include data on the presenting illness and illness severity (e.g., heart rate, respiratory rate, oxygen saturation, physical exam findings, triage level, chief complaint, discharge diagnosis, disposition), lab tests, procedures, interventions, and test results (if any), during these visits and/or hospitalizations.

12.

Follow-up Assessments (Table 1). All participants will be assessed at 6-weeks (T1) during home visits and at 6-months (T2) via phone or email; home visits will be made to conduct biochemical validation of caregivers and children when caregivers report that they have quit at T2. We will use self-report measures of prolonged abstinence and biochemically validated point prevalence at T1 and T2 to assess cessation.⁸⁵⁻⁸⁷ Point prevalence of tobacco use will be measured by the question: “Have you smoked, even a puff, in the last 7 days?” Caregivers will be considered abstainers if they report no tobacco use in the past 7 days. Prolonged abstinence will be measured by the question: “When did you last smoke a cigarette?” Response categories will range from “less than 1 month ago” to “more than 6 months ago.” Secondary outcomes will be assessed, including nicotine dependence, readiness to change, a quit attempt of \geq 24 hours, patterns of smoking, number of cigarettes smoked/day, treatment initiation, NRT or other pharmacotherapies used, QL, text, or web follow-up. As described above, we will use measures of child SHSe to assess children’s exposure and if home/car smoking bans are present. Secondary outcomes pertaining to the child’s SHSe, total home/car smoking bans, and SHSe-related healthcare utilization (PED visits or hospitalizations at CCHMC) will be assessed.

Biochemical Validation. At 6-weeks, we will conduct home visits to: (1) verify abstinence on caregivers who report that they have not smoked in the past 7 days via expired carbon monoxide testing and salivary cotinine (2) obtain

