a follow-up salivary cotinine level on children to validate total home smoking bans, and (3) complete assessment of outcomes. Cotinine is generally accepted to be the best of the available biomarkers, with over 95% specificity and sensitivity, it is noninvasive, and easily obtained in young children.^{85,86} [ENREF 114](#) A standard protocol will be used to collect saliva samples from each child at baseline, 6-weeks, and possibly 6 months. Cotinine analyses will be performed with Enzyme Immunoassay techniques by Salimetrics LLC, State College, PA. In the child samples, the lower limit of cotinine sensitivity is 0.05 ng/ml (range of sensitivity: 0.06-200 ng/ml); undetectable cotinine values will be recorded as 0 ng/ml.^{87,88} Alternatively, if additional funds are available, cotinine analyses may be assessed with liquid chromatography mass spectrometry (LCMS). Caregiver abstinence will be established if the caregiver's expired carbon monoxide level is at or below 6 ppm; salivary cotinine may be assessed to confirm abstinence in caregivers who report they have quit if their exhaled carbon monoxide does not provide verification. At 6 months, we will assess all caregivers via phone or email, and validate self-reported abstinence and total home smoking bans via expired carbon monoxide testing and/or salivary cotinine.

Data Management

Data management will occur at CCHMC. Participants will complete the baseline assessment on a web-enabled tablet research computer. Data will be collected and managed using REDCap (Research Electronic Data Capture).⁹² [ENREF 116](#) The Redcap Mobile App may also be used in order to scan barcodes on samples.

DATA ANALYSIS

Sample Size and Power Estimates

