Sample Size. Our estimate of the number of caregivers that we plan to enroll is based on the average number of unique patients and the smoking prevalence of caregivers seen in a 12-month period in the PED at CCHMC. Based on enrollment in previous studies (which had average annual enrollment of 300-350 caregivers), and a 30 month chart review on the number of annual visits for patients with SHS-related complaints (at least 6,000), we are conservatively expecting to enroll 300 caregivers who smoke over 12 months, for a total of 750 caregivers in 30 months. To obtain the effective sample size for power analyses of outcomes, the sample size must be adjusted for potential attrition of approximately 20% at 6 months, although all efforts will be used to decrease this attrition rate, leaving a total of 600; 300 per group.

Estimate of effect sizes: Evaluation of outcomes. Based on the recommendations of Hughes et al.,^{85,86} we will use 2 criteria for abstinence: 6-month point prevalence and prolonged abstinence at 6-months. Based on a similar prior study, we expect that 6-month point prevalence in the HHC condition will be 6.3%.⁵⁴ For prolonged abstinence, we are basing our estimation on the 2.1% rate for the HHC and 7% rate for SBIRT. We are conservatively estimating a point prevalence cessation rate of 6.3% and prolonged abstinence rate of 2.1% in the HHC group.⁵⁴ We are basing our estimate of 6-month point prevalence of the SBIRT group on the odds ratio derived from meta-analyses assessing the effectiveness of NRT vs. a control, ranging from 1.4-4.6,⁵⁴ to give a cessation rate of 10-12% in the SBIRT group. However, since a clinical counselor/intake coordinator/research coordinator will be conducting the intervention, we expect high compliance in implementation. Thus, we are estimating a cessation rate of 12% in the SBIRT group. Similarly, for prolonged abstinence, we are assuming a rate of 7% in the SBIRT group.

Power (Table 2). Power analyses are based on estimates of differences in both 6-month point prevalence and 6-month prolonged abstinence between groups. With 300 subjects in each group, we would have 80% power to detect an increase of 6.4% in cessation rate. However, assuming a multiple imputation approach, we would be able to detect a 5.5% increase in cessation rate.

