We will use GLMM to evaluate the relative effectiveness of the SBIRT versus HHC group on our primary outcomes: point prevalence and prolonged abstinence at 6-months. The analysis will be repeated with caregiver level differences between groups included as covariates. We will use mixed model analysis of covariance, with repeated measures to assess change (controlling for baseline differences between groups) to assess the effect of the SBIRT on secondary outcomes including reduction in use, number of quit attempts, and changes in readiness to quit. Kappa statistic will be used to assess agreement between the caregiver's self-report and the assessment of tobacco use based on expired carbon monoxide levels and/or salivary cotinine at 6 months. It is possible that use of and adherence to the NRT will influence outcomes in the intervention group. In addition, some of the participants in the control condition may obtain NRT during the study interval. We will examine NRT use or dose, defined as self-reported adherence, as a covariate in order to control for this possible relationship.

Analyses for Primary Aims 1-3.

Primary Aim 1, Hypothesis 1: We hypothesize that SBIRT participants will have higher prolonged abstinence and point prevalence cessation rates compared to those in the HHC group. As stated above, our primary approach to the analysis is using multiple imputation, with clinical counselors/intake coordinators/research coordinators included in the model. We shall then use analysis of covariance, to control for any baseline differences of caregivers between conditions. In addition we will also control for motivation to quit, considered a priori as a potential covariate, using the score on the contemplation ladder. As we are stratifying on motivation to quit and caregiver gender, we will initially enter this into the model as an interaction. To address child cotinine as the 6-month outcome, we will use a t-test and then an analysis of covariance to incorporate the variables different at baseline. Incorporating the 6-week outcome values, we will use GLMM invoking GEE for the repeated

measures and also a model including covariates. This approach will be used to assess the intervention's effect on abstinence and point prevalence and child cotinine.

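### Under the 6-month procedures as written, only caregivers who report abstinence are tested, so the planned kappa on tested caregivers is 0 or undefined whatever share is confirmed

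*Combined protocol and SAP*

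**What the plan says.** All references are to the combined protocol and SAP.

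- **The analysis.** General approach for addressing study aims: "Kappa statistic will be used to assess agreement" between what caregivers report and their tobacco use as classified by expired CO and/or salivary cotinine, at 6 months. No expected value, threshold, precision or analysis set is given.
- **Who is tested at 6 months.** Four places make the test follow from the self-report:
  - Assessments (Study Design Overview): "Should the caregiver report abstinence and smoking bans, a home visit will be conducted to validate self-reported abstinence and total home smoking bans".
  - HHC Protocol, Intervention Materials: the same trigger, "Should the caregiver report abstinence and smoking bans, a home visit will be conducted".
  - Follow-up Assessments (Table 1): "home visits will be made to conduct biochemical validation of caregivers and children when caregivers report that they have quit at T2".
  - Biochemical Validation: "At 6 months, we will assess all caregivers via phone or email, and validate self-reported abstinence".
- **What counts as confirmed.** Biochemical Validation: abstinence is established if the caregiver's "expired carbon monoxide level is at or below 6 ppm". Cotinine may be used for reported quitters whose CO result does not verify the claim.
- **The contrary statement.** Purpose, Primary Aim 1: the primary outcomes at 6 weeks and 6 months are "validated in all participants via expired carbon monoxide and salivary cotinine".

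No 6-month procedure schedules a CO or cotinine test for caregivers who report that they still smoke, and no subsample of them is planned.

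**The concern.** Kappa compares two classifications and needs both to vary. If a test is done only when the caregiver claims abstinence, the self-report among tested caregivers is a constant. Kappa then takes the same value for near-perfect and for poor confirmation.

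Primary Aim 1 presents the abstinence outcomes as self-reports backed by biochemical validation. This kappa is the plan's only caregiver-level statistic on how well the two match. If it carries no information, the trial has no planned numerical summary of how far the self-reports can be trusted, although the tested caregivers do supply usable data on that question.

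**Working it through.** The plan gives no figure for this analysis, so there is nothing to reproduce. The check is algebra, illustrated with the plan's own rates.

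**Inputs** (Sample Size and Power Estimates): 300 caregivers per arm retained at 6 months; expected 6-month point prevalence 6.3% in HHC and 12% in SBIRT.

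Expected self-reported quitters: 300 × 0.063 + 300 × 0.12 = 18.9 + 36 = 54.9, about 55. The other 600 − 55 = 545 report smoking.

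**Formula.** Kappa = (Po − Pe)/(1 − Pe), where Po is observed agreement and Pe is chance agreement from the margins.

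**Tested caregivers only.** Let n reported quitters be tested and a be confirmed. The row for reported smokers is empty.

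- Po = a/n.
- Pe = 1 × (a/n) + 0 × ((n − a)/n) = a/n.
- So Po − Pe = 0. Kappa = 0 when a < n, and 0/0 when a = n.

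| Confirmed of 55 | Po | Pe | Kappa |
|---|---|---|---|
| 55 | 1.000 | 1.000 | undefined |
| 50 | 0.909 | 0.909 | 0 |
| 44 | 0.800 | 0.800 | 0 |
| 28 | 0.509 | 0.509 | 0 |
| 11 | 0.200 | 0.200 | 0 |

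**If reported smokers were tested as well.** The documents give no rate at which reported smokers would test negative, so 0%, 5% and 10% are assumed.

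| Confirmed of 55 | 0% negative | 5% negative | 10% negative |
|---|---|---|---|
| 50 | 0.95 | 0.73 | 0.58 |
| 44 | 0.88 | 0.66 | 0.52 |
| 28 | 0.65 | 0.46 | 0.34 |

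For example, with 44 confirmed and 27 of 545 negative, Po = (44 + 518)/600 = 0.937, Pe = (55 × 71 + 545 × 529)/600² = 0.812, and kappa = 0.66. Kappa now responds to the true agreement, which the planned data do not allow.

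**What the planned data can estimate.** The proportion confirmed among reported quitters. With 50 of 55 confirmed this is 91%, Wilson 95% interval about 80% to 96%, where kappa gives 0.

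**Precision by arm.** With 18.9 and 36 reported quitters and an assumed 90% confirmed in each arm, the 95% half-width for the difference is 1.96 × √(0.9 × 0.1/18.9 + 0.9 × 0.1/36) = 1.96 × 0.085 = 0.167, about ±17 percentage points.

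**The case against.** Three ways out deserve an answer.

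1. **Primary Aim 1 says all participants are validated.** If every caregiver were tested at 6 months, kappa would be estimable, and the documents do not say which text governs. This stands to the extent that the conclusion is conditional on the detailed procedures. But no 6-month procedure carries out universal testing. Even at 6 weeks, the 100% verification described under Assessments applies to caregivers who say they have not smoked in the past 7 days. The texts need reconciling either way.

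2. **The trigger is ambiguous.** Assessments and the HHC Protocol tie the visit to a report of abstinence and bans together. Read as either claim, a caregiver who still smokes but reports a ban might be visited and tested, so self-report would vary. Follow-up Assessments, which refers to reported quitting alone, makes this less likely. Any such caregivers would also be a selected group, unsuitable for estimating agreement.

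3. **Untested reported smokers could be counted as smokers.** Kappa would then be 0.65 to 1.00 for 28 to 55 of 55 confirmed, not 0. But the plan does not state this rule, and it would supply 545 of 600 classifications by assumption.

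A reader might also infer that a reported kappa of 0 would discredit the primary outcome. The documents do not support that. Kappa is attached to no decision rule, the arms are compared with mixed models and multiple imputation without it, and an empty row would be plain once the table was drawn up.

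**Conclusion.** The point holds conditionally. If the 6-month procedures govern and kappa is computed on tested caregivers, it is 0 for any confirmed share below 100% and undefined at 100%. The algebra is exact and does not depend on the illustrative 55 quitters.

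It would go too far to say that kappa cannot work under any reading of the documents, or that the Primary Aim 1 wording is necessarily the mistake. What can be said is that this wording and the 6-month procedures conflict, and that the planned kappa is informative only if reported smokers are tested too. The damage is limited to the validation analysis. The treatment comparison is unaffected, but the only planned caregiver-level check of self-report against the biochemical result would tell the reader nothing.

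**What to change.** - **Replace kappa** with the proportion of self-reported quitters at 6 months who are confirmed under the Biochemical Validation definition (CO at or below 6 ppm, or salivary cotinine where CO does not verify). Report it overall and by arm, with 95% confidence intervals, and give the arm difference. A CO-only definition would depart from the plan and could count cotinine-verified quitters as unconfirmed.
- **State the denominator.** Show separately the reported quitters who could not be tested, since the HHC Protocol allows phone or email assessment when a home visit is not possible.
- **Align the text.** Change Primary Aim 1 to say that validation is in caregivers who report abstinence, and use one trigger for the 6-month visit throughout.

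**Cost.** Primary Aim 1 is protocol text, so this is a minor amendment. Report of Changes or Amendments to the Protocol requires IRB approval for it. No extra data collection is needed. The arm difference will be too imprecise to exclude moderate differential misreporting, and the report should say so.

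**Alternative.** To keep kappa, all reported smokers, or a random subsample weighted back, would also have to be tested at 6 months and the procedures amended to match. That needs additional visits and assays.

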Caregiver smoking is an important cause of morbidity and mortality in both adult smokers and their children who are involuntarily exposed to secondhand smoke (SHSe). Our research has found that caregivers who visit the Pediatric Emergency Department (PED) with their children have a high prevalence of smoking (up to 48%), their children have high levels of SHSe equivalent to that of active smokers, and they regularly use the PED for nonurgent, SHSe-related complaints. These smokers are motivated to quit and eager to receive cessation counseling in this setting. Annually, more than 3 million PED visits involve treatment of children with SHSe-related illnesses. These visits provide a unique “teachable moment” to motivate caregiver quitting, given the relationship between quitting and improvements in their child’s health. Because of the long, unavoidable wait times and the frequent use of the PED for non-urgent care, this is an ideal venue for intervening with this population. Moreover, we and others have demonstrated the feasibility of conducting complex randomized trials in PEDs without disrupting clinical flow. Building on our prior research, we propose to conduct the first randomized trial to test whether a cessation intervention in the PED setting can reduce caregiver smoking and decrease children's SHSe. This study will test the efficacy of a cessation intervention for caregivers in a large, inner-city PED that is a major nodal site for the federally funded Pediatric Emergency Care Applied Research Network (PECARN). The proposed Screening, Brief Intervention, and Assisted Referral to Treatment (SBIRT) will highlight the effects of SHSe on their child’s health. We will randomize 750 caregivers who smoke who present to our PED with their child who has a SHSe-related illness to either one of two conditions: 1) SBIRT; or 2) Healthy Habits Control (HHC). The SBIRT condition will use components shown to be effective in the out-patient setting but not yet tested in the PED setting. It will include a brief form of the Clinical Practice Guideline: Treating Tobacco Use and Dependence, motivational interviewing, engaging and personalized materials on the effects of smoking and SHSe, immediate access to caregivers’ choice of cessation resources (e.g., Quitline, smokefree.gov, or smokefreeTXT), a 12-week supply of nicotine replacement therapy and booster materials for 12 weeks. The HHC program has been previously developed and used in the out-patient setting, and will be used as an attention control in which caregivers will receive instruction on healthy lifestyle choices to improve their child’s health. Cessation assistance will be offered at the study’s conclusion. If effective, the SBIRT model could be routinely used in the PED setting, which could reach at least one million smokers a year, and could result in significant reductions in caregivers' tobacco use, SHSe-related pediatric illness, and costs in this population. In addition, our results will inform the conduct of public health research efforts aimed at adults via the PED. If successful, we will create a comprehensive package of materials for disseminating the implementation of the intervention throughout PECARN and non-PECARN PEDs, and EDs nationwide. This study will also assess the prevalence and correlates of cannabis smoke exposure (CSE) among PED patients who are in the SHS-exposed group.

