Primary Aim 2, Hypothesis 2: We will evaluate the effectiveness of the SBIRT on total home/car smoking bans and on child SHSe which will be measured by both caregiver report and child salivary cotinine, as recommended by Halterman et al.⁸⁷ The reliability of caregiver's reports will be examined by comparing amount of smoking and SHSe levels reported at 6-months using Pearson's correlations. For validation, we will compare the child's salivary cotinine concentrations for those reporting total home/car smoking bans and those not, we shall also examine the change in cotinine levels from baseline for those initiating bans versus not. The computational procedure will use data from the 2 measurement points, controlling for the within-subject correlation of measures repeated over time.^{97,98} The main analysis will use GLMM, first to assess the intervention effect alone and then including covariates. First, we will investigate immediate intervention effects based on change from baseline to 6-weeks post-intervention. Next, we will investigate change from 6-weeks to 6-months to examine maintenance effects. To examine overall change, we will use GEE, examining linear and quadratic terms for time, group, and group \times time interactions as explanatory variables.⁵² Use of NRT, described above, may be of particular interest as a covariate for this analysis.

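### Self-reported NRT use, a post-randomisation part of SBIRT, is to be examined as a covariate to control for its influence, and nothing keeps that model out of the efficacy conclusions

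*Combined protocol and SAP*

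**What the plan says.** The general approach for addressing study aims, which precedes the analyses for each aim, gives two reasons for looking at NRT. Use and adherence may influence outcomes in the intervention group, and "some of the participants in the control condition may obtain NRT during the study interval". It then states the rule: "We will examine NRT use or dose, defined as self-reported adherence, as a covariate in order to control for this possible relationship".

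Under Primary Aim 2, Hypothesis 2, the plan says: "The main analysis will use GLMM, first to assess the intervention effect alone and then including covariates". The paragraph ends: "Use of NRT, described above, may be of particular interest as a covariate for this analysis".

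For Primary Aim 1, Hypothesis 1, the plan says that "our primary approach to the analysis is using multiple imputation", with the interventionist in the model. Baseline differences follow, and then motivation: "In addition we will also control for motivation to quit, considered a priori as a potential covariate, using the score on the contemplation ladder". NRT is not named in these steps.

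Four other places bear on what kind of variable NRT use is:

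- The abstract lists among the SBIRT components "a 12-week supply of nicotine replacement therapy and booster materials for 12 weeks". The Assist step of the SBIRT protocol offers a free six-week supply at baseline, and a second six weeks to those who used about 80% of the first.
- Participant Screening, Enrollment, and Exclusion rules out caregivers already on drug treatment for cessation.
- Outcome Measures lists use of NRT as a secondary caregiver outcome.
- The mediation analysis under Aim 3 does not list NRT use among the mediators.

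**The concern.** NRT use is a consequence of allocation. One arm is given NRT, and users at entry are excluded, so use in the trial develops after randomisation. Dose also reflects later behaviour, because the second supply depends on how much of the first was used.

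Putting such a variable in the model changes the question. The arm coefficient then compares SBIRT and HHC caregivers with the same NRT use, which leaves out the part of the SBIRT effect that runs through NRT. It also breaks the protection of randomisation. Caregivers who use NRT without being given it, and those who decline it when it is free, are likely to differ in motivation. The plan does measure motivation: "We will stratify by gender of the primary caregiver and stage of readiness to quit smoking", plus the contemplation-ladder score. Baseline readiness can reduce this confounding only in part.

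Neither stated reason supports the adjustment as a way to judge efficacy. That NRT influences outcomes in the SBIRT arm is how the package is meant to work. NRT use among controls is a fair supplementary question, but a covariate does not correct for it. If NRT helps, control use narrows the contrast between arms, so a correction would widen it. Adjustment narrows it further.

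At stake is a controlled arm effect that looks weak although the package worked, reported without any statement that it does not test Hypothesis 1 or 2.

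**Working it through.** No figure in the plan depends on this rule, so there is none to reproduce. The check is a reading of the sections above plus an illustration of size.

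**Inputs from the documents** (Sample Size and Power Estimates): 6-month point prevalence 6.3% in HHC and 12% in SBIRT; 300 per arm after 20% attrition; NRT-versus-control odds ratios of 1.4 to 4.6.

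**Assumptions:** NRT uptake by arm (SBIRT/HHC) of 30%/5%, 50%/10% or 60%/5%. The 1.4 to 4.6 range is used as a user-versus-non-user odds ratio. The plan uses it at arm level, to reach an SBIRT rate of 10-12% (arm odds ratio 1.65 to 2.03). Confounding by motivation is not modelled.

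**Unadjusted effect.** OR = (0.12/0.88)/(0.063/0.937) = 2.03. Expected counts are 36 and 264 in SBIRT, and 18.9 and 281.1 in HHC. SE of log OR = √(1/36 + 1/264 + 1/18.9 + 1/281.1) = 0.297.

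**Adjusted effect.** Model: logit P(abstinent) = a(arm) + b × NRT, with b = ln(NRT OR). For uptake u and arm rate p, a is solved from (1 − u)·expit(a) + u·expit(a + b) = p. The adjusted arm OR is exp(a_SBIRT − a_HHC), and its SE comes from the expected information.

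**One case in full: uptake 50%/10%, NRT OR 2.0.**

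- HHC: a = −2.790, so non-users 5.78% and users 10.94%. Check: 0.9 × 5.78 + 0.1 × 10.94 = 6.30%.
- SBIRT: a = −2.384, so non-users 8.44% and users 15.56%. Check: 0.5 × 8.44 + 0.5 × 15.56 = 12.00%.
- Adjusted log OR = −2.384 + 2.790 = 0.406, so OR 1.50, SE 0.33.
- Share carried by NRT alone: applying 50% uptake to the HHC intercept gives 0.5 × 5.78 + 0.5 × 10.94 = 8.36%, and (8.36 − 6.3)/5.7 = 36%.
- Control NRT use set to zero, SBIRT kept at 12%: HHC becomes 5.78% and the OR (0.12/0.88)/(0.0578/0.9422) = 2.22.

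**All cases:**

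| Uptake SBIRT/HHC | NRT OR | Adjusted arm OR | SE | Share carried by NRT alone | Arm OR, control NRT use zero |
|---|---|---|---|---|---|
| 30%/5% | 1.4 / 2.0 / 3.0 / 4.6 | 1.85 / 1.66 / 1.44 / 1.21 | 0.31-0.33 | 10-69% | 2.07 / 2.12 / 2.21 / 2.34 |
| 50%/10% | 1.4 / 2.0 / 3.0 / 4.6 | 1.76 / 1.50 / 1.24 / 1.00 | 0.33-0.35 | 16-100% | 2.11 / 2.22 / 2.40 / 2.66 |
| 60%/5% | 1.4 / 2.0 / 3.0 | 1.67 / 1.34 / 1.03 | 0.36-0.39 | 22-95% | 2.07 / 2.12 / 2.21 |

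At 60%/5% an NRT OR of 4.6 is left out, because above about 3.1 NRT alone would carry more than the whole planned difference.

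**Cross-check by another route.** Fix the share of the effect that runs through NRT and vary uptake over 40%/5%, 60%/10% and 80%/10%. If none runs through NRT, the adjusted OR stays at 2.03 but its SE rises from 0.297 to 0.32-0.40. If half does, the adjusted OR is 1.45 to 1.48. If all does, it is 1.00.

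Every adjusted OR in the table is below 2.03, and every OR with control NRT use removed is above it.

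**The case against.** The strongest reply is that the plan does not make the NRT-adjusted model primary. The Aim 1 steps are named and omit NRT. The Aim 2 model with the intervention alone is fitted first. The verbs are weak, and looking at adherence or dose is a common supplementary analysis. All of this stands, and it is why the point is not graded higher. What remains is the stated purpose, which is control, together with the absence of any label or limit on the result.

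The last Aim 2 sentence is also ambiguous. It may refer to the two-step main analysis, or to the GEE for overall change in the sentence just before it. That makes little difference, because the GEE also estimates group and group-by-time effects for Hypothesis 2.

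Setting control NRT use to zero is a target the documents never state, so the comparison does not show that the plan tried that correction and failed. It shows only that the second stated reason gives no support to the adjustment, because a correction for control use would move the other way.

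The size rests on invented uptake, and the lowest adjusted odds ratios arise where NRT is assumed to carry nearly all of the effect. The illustration concerns point prevalence, whereas the risk of misreading is clearest in Aim 2. That is fair: the figures support the direction and a plausible range, and no size is claimed for bans or for prolonged abstinence.

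**Conclusion.** The concern holds. The plan states a rule to control for a post-randomisation component of the intervention, on reasons that do not support it, and does not say that the resulting arm effect is no test of Hypothesis 1 or 2. The as-randomised effect is still estimated, so the fault lies in the rationale and in how the adjusted result could be read, most clearly in the covariate step of Aim 2.

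For point prevalence, an odds ratio of 2.03 becomes 1.85 to 1.00 over the settings examined. The direction needs only that NRT helps and is used more in SBIRT than in HHC. The amount depends on assumed uptake, on reading 1.4 to 4.6 as a user-versus-non-user odds ratio, and on no confounding by motivation. The change should be made; confidence is medium.

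**What to change.** - In the general approach for addressing study aims, delete the clause that gives control for this relationship as the purpose of the NRT covariate.
- There and under Primary Aim 2, Hypothesis 2, state that conclusions on Hypotheses 1 and 2 come from as-randomised models that do not include NRT use, and that NRT use is not part of the covariate step of the Aim 2 main analysis.
- Label any model containing NRT use, including one on NRT obtained by controls, as exploratory and not a test of Hypothesis 1 or 2.
- Optionally, add NRT use to the mediators under Aim 3.

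The cost is wording in two places. The planned models without NRT are unchanged. The mediator analysis would be extra work and is not needed for the fix.
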